mm diameter ring with the treatment,⁴⁰ the national design that was presented has a uniform +3.50 diopter power zone that alters the visual field by 5% at 10 degrees from the circular shaped fovea,³⁸ as presented at the International Myopia Conference a month ago. As it is known that positive defocus in 30-40 minutes of exposure modifies the axial length (measured with Lenstar) by 10 microns due to changes in the choroidal thickness,⁴² The national design has been tested on 17 volunteer subjects showing a significant change of 11 microns in the axial length of their eyes, suggesting this pilot study (in the process of being published) that the lenses should be effective in halting the progression of myopia, as changes in the choroid are the first event in the retinal message that governs ocular growth.⁴³ This, coupled with the survey that gave a good reading tolerance in 70% of the 17 respondents within a month of wearing them, was presented at the Conference and is in the public domain. Respondents found it difficult to walk around with these lenses because they are like an executive bifocal, but tolerated them well for reading at home, with small lateral movements of the head when reading A4 texts or the computer. It is therefore our intention to do a free field test with such lenses on a larger sample.

POPULATION

Consecutive patients between 8 and 16 years of age who attend the institutions accredited for this study. These institutions will be accredited only if they can perform routine studies for myopia control (refraction exam and optical biometry).

USE OF GLASSES

Once the eyeglass prescription has been written by the ophthalmologist, the enrolled patients will be seen in opticians accredited for this study in close proximity to the

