agree to take the test for one year, with no ocular pathology other than myopia, with spherical equivalent (sphere + 50% of the cylinder) between -0.50 D and -5.00 D, with astigmatism less than -2.00 D in each eye, with anisometropia less than -1.00 D, with keratometry less than 47.00 D in the most curved meridian. Genetic syndromes will not be included or ruled out. A complete ophthalmologic evaluation will be performed including tonometry, fundus, subjective refraction and refraction under cycloplegia with two drops of 1% cyclopentolate instilled 5' apart and performed 40' after the last drop. Visual acuities of the subjective refraction will be greater than 8/10 in each eye. Axillary length measurements with optical biometry will be performed at the beginning of treatment at follow-up and at the end of the study. New cycloplegic refractions will be performed during follow-up and at one year of treatment. A survey of habits and history, including reading, outdoors, ON-OFF contrast use, hours of schooling, age of onset of spectacle use and family history of high myopia (also likely use of devices to monitor these habits in selected group) will be conducted. A pair of spectacles and their frames will be provided free of charge to all children studied for one year with the special addendum of peripheral defocus treatment or laser treatment for contrast reduction depending on the treated group. The children will be instructed to wear the glasses especially in front of smartphones, tablets, PC's or books at home after five o'clock in the afternoon and until going to bed, every day of the week including Saturdays and Sundays. During the rest of the day they will use their usual correction without properly updated defocus. As defocus in experimental animals has more effect in stopping experimental myopia in the afternoon than in the morning,⁴⁴ It is expected that use in the afternoon only will be sufficient to achieve the effect. On the other hand, the peripheral contrast-lowering lens that has shown good tolerance and absence of visual field alteration will be used all day long by the subjects under treatment.

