Adherence will be evaluated at the one-year follow-up and will be reported as the number of cases that failed to complete the three scheduled visits in one year with respect to the total number of cases that were enrolled in compliance with the first visit and the delivery of the spectacle. Tolerance of these glasses will be assessed with a tolerance questionnaire that is presented in the attached medical record. This questionnaire has already been tested on 24 subjects aged 18 to 24 years in a pilot trial presented at the International Myopia Conference, as explained in the previous section on the defocus spectacle, showing good tolerance in these subjects. Some tests in younger children that were performed in the last months show that tolerance is very good in them, since minors have greater plasticity and adaptability than young adults previously tested. Tolerance and adherence will be classified as GOOD / BAD, in a dichotomous way, with the cut-off according to the answer given by whether the child tolerated them well or not. On the other hand, tolerance will also be evaluated in dichotomous form with responses to reading and walking

performance.

PROCEDURES TO GUARANTEE ETHICAL ASPECTS

The anonymity of all participants will be preserved. Patients' names will be removed from the database for statistical analysis. The only ones who will know the names of the patients are the physicians involved in their primary care, and they will have to keep the information in their respective institutional medical records and enter the data necessary for the research in a web form designed by the sponsoring company.

The Declaration of Helsinki and its modifications, the Good Clinical Practices guide, the harmonization norms and the resolution of the Ministry of Health 1480/11 will be observed and taken into account as guidelines (See informed consent ANNEX VI). It is stated for the record that the principal investigator does not have any type of conflict of interest since the patenting of the defocus glasses is the responsibility of the sponsor's company.

SAFETY PRECAUTIONS

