Do you take tutoring outside of school? (Circle) YES NO

How many hours do you spend outdoors when you leave school?Hs

How many hours per day do you spend reading books or doing homework?
.....Hs

How much time per day do you spend playing with your cell phone or tablet?
.....Hs

ON ANY SATURDAY OR SUNDAY.....

How many hours per day do you spend reading books or doing homework?Hs

How many hours per day do you spend outdoors on a weekend day?Hs

How much time per day do you spend playing with your cell phone or tablet?
.....Hs

PART II EYEGLASS DELIVERY

DATE

PART II. BIS (ATTACHMENT QUESTIONNAIRE)
AT THE MONTH OF DEFOCUS EYEWEAR DELIVERY (TELEPHONE SURVEY)
DATE

Have you worn the glasses at home during this month? YES NO

Have you worn glasses all day this month? YES NO

If you answered "YES" to any of the above, continue with these

In general, do you tolerate them well? YES NO

Have you ever had trouble turning your head to look sideways? YES NO

Out of the seven days of the week, how many days do you not use them?.....

Have you ever had trouble turning your head to look down when reading? YES NO

Have you ever had trouble turning your head to look down when walking? YES NO

PART III

DATE SECOND VISIT AFTER SIX MONTHS.....

EYE DER SPHERICALCILINDRICAL AXIS.....

SPHERIC IZQ EYE.....CILINDRITRIC AXIS.....

AXIAL LENGTH OD..... OI.....

PART III (BIS) SIX MONTH ADHERENCE QUESTIONNAIRE

Have you worn your glasses at home during this month? YES NO

Have you worn glasses all day during this month? YES NO

If you answered "YES" to any of the above continue with these.....

In general, do you tolerate them well?

YES NO

Have you found it difficult to turn your head to look sideways? YES NO

Of the seven days of the week, how many days do you not use them?

Did you have trouble turning your head to look down when reading? YES NO

Have you had trouble turning your head to look down when walking? YES NO

PART IV

DATE THIRD VISIT AT TWELVE MONTHS.....

RIGHT EYE SPHERICALCILINDRICAL AXIS.....

LEFT EYE SPHERICAL.....CYLINDRICALAXIS.....

AXIAL LENGTH OD..... OI.....

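### The walking-tolerance item has no answer for a child who does not walk in the glasses, so a NO cannot be interpreted, especially at month 6

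*Combined protocol and SAP*

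**What the plan says.** All references are to the combined protocol and SAP. Tolerance and adherence form the primary objective (Objectives). Under Evaluation of Tolerance and Adherence, the overall GOOD/BAD rating follows the child's general answer on whether the glasses were tolerated. The section then adds a separate measure: "tolerance will also be evaluated in dichotomous form with responses to reading and walking" performance.

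The walking item at month 1 (Part II BIS) is "Have you ever had trouble turning your head to look down when walking? YES NO". At month 6 (Part III BIS) it is "Have you had trouble turning your head to look down when walking? YES NO". Both are reached by a YES to either of two wear questions. The first, in its month-1 form, is "Have you worn the glasses at home during this month? YES NO"; the second asks about all-day wear.

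On exposure to walking, the documents say three things:

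- **Methods:** children are told to "wear the glasses especially in front of smartphones, tablets, PC's or books at home after five o'clock in the afternoon", and to use their ordinary correction for the rest of the day.
- **Defocus Glasses of National Design:** "Respondents found it difficult to walk around with these lenses because they are like an executive bifocal". The same pilot reports good reading tolerance in 70% of 17 respondents but gives no percentage for walking.
- **Use of Glasses:** the optician checks adaptation and mobility in the shop, then tells the child to wear the glasses at home for a couple of days and afterwards as much as they can.

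Neither the tolerance section nor the Plan for Analysing the Results gives a scoring key or denominator for the walking item, or a rule for a child who did not walk in the glasses.

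**The concern.** Home wear alone opens the walking question, and the instructed home use is largely seated. A child can therefore be asked about trouble in an activity never done in the glasses, with no answer that says so. If that child is recorded as NO and counted with those who walked comfortably, the error makes walking tolerance look better than it was among children who walked. It falls on the one activity in which the plan's own pilot reports difficulty. Because no other item records whether the child walked in the glasses, the analyst cannot repair this afterwards.

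**Working it through.** There is no stated figure to reproduce; the point rests on the form's wording.

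**Step 1. What each child would answer.**

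| Child's experience | Month 1 (*ever*) | Month 6 (no *ever*) |
|---|---|---|
| Walks in them, no trouble | NO | NO |
| Walks in them, trouble | YES | YES |
| Tried, had trouble, stopped | YES | YES or NO, by how the question is read |
| Never walked in them | NO or blank | NO or blank |

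At month 1 only the last row is mixed with the first. At month 6 the third row may be mixed in as well: the wear questions just before it ask about the current month, and the walking item no longer says *ever*.

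**Step 2. Size.** Let f be the share of wearers who do not walk in the glasses and answer NO, and t the trouble rate among those who walk. Both are assumptions.

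- Apparent walking tolerance = 1 − (1 − f) × t
- Walking tolerance among walkers = 1 − t
- Excess = [1 − (1 − f) × t] − (1 − t) = f × t

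| t | Among walkers | f = 0.2 | f = 0.4 | f = 0.6 | f = 0.8 |
|---|---|---|---|---|---|
| 0.3 | 70% | 76% | 82% | 88% | 94% |
| 0.5 | 50% | 60% | 70% | 80% | 90% |
| 0.7 | 30% | 44% | 58% | 72% | 86% |

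The smallest excess is 0.2 × 0.3 = 6 points and the largest is 0.8 × 0.7 = 56 points.

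**Step 3. In children.** Take the planned 50 as if all answered, with f = 0.6 and t = 0.5. Then 50 × 0.6 = 30 do not walk in the glasses and 20 do. Of the 20, 10 answer YES and 10 NO. The form shows 30 + 10 = 40 NO answers, or 40/50 = 80%. Among walkers the figure is 10/20 = 50%.

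If non-walkers who avoid walking because the glasses bother them also counted against tolerance, the figure would depend on how many of the 30 they are. With none it is 10/(10 + 10) = 50%; with all 30 it is 10/(10 + 10 + 30) = 20%. The same 80% on the form is compatible with anything from 20% to 50%.

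**The case against.** Several arguments limit the point, and most of them stand in part.

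- **Avoidance at month 1.** A reader might infer that children who take the glasses off to walk because they tolerate them badly will truthfully answer NO. At month 1 the word *ever* works against that: a child who tried and gave up has had trouble and should answer YES. This stands, and leaves only children who never tried. It does not help at month 6.
- **Some walking is likely.** The shop mobility check, the optician's instruction and the all-day wear question all point to some exposure, and the Methods make near work the main use, not the only one. This stands, so f is unknown and may be small. The all-day question does not settle it: a NO there does not show whether the child walked in the glasses at home, and the plan does not link it to the walking result.
- **The overall rating.** A reader might infer that a non-walker is classed as tolerating the glasses overall. The documents do not support that: the GOOD/BAD cut-off uses the general question.
- **Scoring is inferred.** Nowhere is NO defined as tolerated, and a caller at month 1 could clarify the answer or leave it blank. This is correct, but NO as tolerated is the natural reading of a dichotomous trouble item, and no rule covers a blank.
- **Choice of target.** A child who stays seated as instructed has no walking trouble under that use. That is fair; the excess is relative to children who walked, and the plan does not say which target it means.
- **Use of the result.** A reader might infer that a low trouble rate would be used to justify wider wear. No passage proposes this, and no threshold or test is tied to the item.

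**Conclusion.** The point holds as a defect of measurement in the separate walking outcome under the primary objective. As written, the form merges children who walked without trouble with children who did not walk in the glasses. Counting the latter as NO overstates walking tolerance, relative to walkers, by f × t.

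The range of 6 to 56 points rests entirely on assumed values of f and t, on non-walkers answering NO and not leaving a blank, and on NO being scored as tolerated. It shows how far the figure could move and is not an estimate of the bias. The problem is greatest at month 6. It is a cheap improvement worth making before data collection. Extending it to the reading item would add little, since reading at home is the instructed use.

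**What to change.** In Part II BIS and Part III BIS, give the walking item a third answer, *does not walk with these glasses on*, with a reason tick: *because they bother me* or *only uses them sitting*.

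Under Evaluation of Tolerance and Adherence, define walking tolerance as NO / (YES + NO + avoided because they bother me), and report separately the number who only use the glasses sitting. A child who tried walking and stopped then counts against tolerance whether recorded as YES or as avoiding.

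The wear instructions in Use of Glasses and in Methods differ and must be reconciled, because they bear on how many children would be expected to walk in the glasses.

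The cost is a few answer options in a web system that Safety Precautions describes as still to be developed, plus a sentence or two in the protocol. No visits or subjects are added. The drawbacks are a smaller denominator, a probably less favourable figure, and slightly less comparability with the questionnaire tested on 24 pilot subjects.

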Given the above-mentioned background, the following study has been designed to evaluate the arrest of myopia progression with the daily use of nationally designed glasses, comparing such progression with a virtual control group of similar age in a population of myopic children and adolescents of the same environment in our country.

WORKING HYPOTHESIS

The nationally designed lenses can be as effective as the proven international industry designs that have been subjected to controlled trials against natural history of the disease.

PURPOSE

To treat a group of consecutive volunteer patients who choose between the affordable treatment in our environment (daily diluted atropine drops for several years) or the special lenses for myopia control designed by the National Industry. The purpose is to compare the progression during one year with the national lenses with respect to the progression with the foreign lenses and/or with the natural history of a virtual control group.

OBJECTIVES

Primary

To assess whether the intervention with locally designed spectacles is well tolerated and adhered to with daily use in childhood and adolescence.

Secondarily

To assess whether intervention with locally designed glasses can control myopia progression in childhood and adolescence.

DEFOCUS GLASSES OF NATIONAL DESIGN

The design of the national defocus lens is based on the original design presented by Carly Lam,⁴⁰ with a 9 mm central zone for distance correction and a correction ring with a +3.50 dioptre defocus between 9 and 32 mm in diameter to act in principle on the para foveal zone which is the one that detects the defocus that governs the growth of the eye.⁴¹ Instead of peripheral defocusing micro lenses that do not alter the visual field in the area of the 32

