ophthalmology offices that are members of the research team. The opticians and ophthalmologists will be asked to watch a video on myopia control developed by the principal investigators where this treatment methodology is explained during the evaluation process at the center of care. The opticians will verify the optical centration in the frames chosen ad hoc, with a modern digital centration system provided by the sponsors. After 15 days, when the glasses with the correct centering are ready, the subjects will go to the optician's office to try on the glasses in that room. On this occasion, as always in these cases, the optician will evaluate the subject's adaptation and mobility in the optician's shop, instructing the child to wear the glasses at home for a couple of days and then to wear them for as long as possible.

SAMPLE AND SAMPLE SIZE

The sample size will be 50 subjects of both genders to compare with the studies abroad that consist of an n between 40 and 90 subjects and the natural history in our country that counted 114 subjects. There will be a group of subjects who will be treated with the nationally designed defocus glasses. Statistical calculation for a difference of 0.25 diopters in progression with respect to controls, for a standard deviation of 0.50 diopters gives an $n = 31$ subjects and taking into account a 20% loss to follow-up the n should equal 38 subjects in the group. Thus reaching 50 subjects exceeds expectations.

METHODS

This field study to test tolerance and percentage of effectiveness of defocus lenses in the control of myopia will include boys and girls from 8 to 15 years of age who voluntarily

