One month after the delivery of the spectacle, the principal investigator in charge will make a telephone call to the parent of the study subject conducting the tolerance survey and thus verifying adherence to spectacle use. The survey is detailed in the attached medical record and responses will be uploaded into the computerised web-based system that will be developed for this study. The system will automate the alerts for these safety calls with automatic emails sent to the principal investigator in the month of spectacle delivery.

PLAN FOR ANALYSING THE RESULTS

The results of numerical variables shall be expressed as mean and standard deviation or median and interquartile range according to whether they are normally or skewed. Nominal variables will be expressed as absolute frequency and percentage. For the comparison of numerical variables, Student's t-test or Mann Whitney U-test will be used as appropriate. Nominal variables will be compared using the Chi-square test or Fisher's exact test as appropriate. A p-value of $p \leq 0,05$.

HUMAN RESOURCES

[name] and [name] are in charge of the design and control of the research. Statistical analysis will be performed by [name]. Physicians accredited to treat patients will have to demonstrate the ability to perform routine consultations for myopia control, refraction studies under cycloplegia and optical biometry. Once accredited, they will have a username and password to upload their data into the web form. Accredited doctors will be in permanent communication with doctors [name] and [name]. There will be a myopia progression monitoring system within the computerised system that will send reports if any child progresses more than 0.25 dioptres in six months to alert researchers so that precautionary measures can be taken in such cases.

MATERIAL RESOURCES

Optotypes, Retinoscope, Autorefractometer and Biometer posters of accredited institutions.

Approximately four institutions with a high turnover of paediatric consultations are expected to be accredited for an estimated enrolment time of 6 months.

Peripheral defocus spectacles will be provided by the sponsor (NOVAR) free of charge to all study subjects for one calendar year with the possibility of extending the study for two years. At the end of the study, if the expected positive results are found, the glasses will remain in the possession of the study subjects.

FINANCIAL RESOURCES

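### The primary tolerance and adherence results are single-arm proportions, but the analysis plan gives them no confidence interval and the sample-size section states no precision for them

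*Combined protocol and SAP*

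**What the plan says.** The Objectives section gives the primary aim as "To assess whether the intervention with locally designed spectacles is well tolerated and adhered to with daily use in childhood and adolescence". The secondary aim is "To assess whether intervention with locally designed glasses can control myopia progression in childhood and adolescence".

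The section Evaluation of tolerance and adherence makes the primary outcomes binary: "Tolerance and adherence will be classified as GOOD / BAD, in a dichotomous way". Reading and walking performance are also to be judged dichotomously. Adherence is to be "reported as the number of cases that failed to complete the three scheduled visits in one year", relative to all children who were enrolled, attended the first visit and received the spectacles.

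The Plan for analysing the results covers such variables in two sentences. One is "Nominal variables will be expressed as absolute frequency and percentage". The other assigns comparisons of nominal variables to the chi-square or Fisher exact test.

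Sample and sample size describes one group treated with the defocus glasses and gives one calculation: "Statistical calculation for a difference of 0.25 diopters in progression with respect to controls", "for a standard deviation of 0.50 diopters". This yields 31, then 38 after allowing for 20% loss, and the section closes: "Thus reaching 50 subjects exceeds expectations".

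**The concern.** With one group and a binary outcome, the primary result is an estimated proportion. An interval shows how far that proportion may lie from the rate in similar children. The plan asks for none, and nowhere mentions a confidence interval, a standard error or a precision target.

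The named tests do not fill the gap. Chi-square and Fisher tests need something to compare with, and the virtual control group is described only as a source of progression data.

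The sample-size section does not help either, because none of its inputs concerns tolerance or adherence. The protocol says nothing about how precisely the planned number of children will answer its primary question.

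This matters because the study is motivated by a tolerability question. The section on the defocus glasses reports good reading tolerance in 70% of 17 pilot respondents, records difficulty walking with the lenses, and gives this as the reason to test them in more people. The gain from more people is precision, and the plan does not report it.

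**Working it through.** **Reproducing the plan's own figure.** Inputs from Sample and sample size: difference 0.25 D, standard deviation 0.50 D. Power and sidedness are not stated; I assume 80% power and two-sided 5%.

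- One-sample formula: n = (SD × (z₀.₉₇₅ + z₀.₈₀) / difference)² = (0.50 × (1.960 + 0.842) / 0.25)² = 31.4, against the stated 31.
- Loss allowance: 31 × 1.2 = 37.2, rounded up to the stated 38. (Dividing by 0.8 gives 38.75, that is 39; the difference is immaterial here.)

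So 31 and 38 come from progression inputs alone.

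**Precision for the primary proportions.** Inputs:

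- N = 50, from Sample and sample size.
- N = 100, from the end of Current state of research, which proposes that number of children.
- Rate of 70%: the pilot reading-tolerance figure.
- Rate of 80%: what 20% loss would imply for adherence as defined, 40 of 50 completing.
- Rate of 90%: a more favourable case.

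The approximate half-width is 1.96 × √(p(1 − p)/N). For 70% and N = 50 this is 1.96 × √(0.21/50) = 1.96 × 0.0648 = 0.127.

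| Observed | Approximate half-width | Wilson 95% CI | Exact (Clopper-Pearson) 95% CI |
|---|---|---|---|
| 35/50 (70%) | 12.7 points | 56.2% to 80.9% | 55.4% to 82.1% |
| 40/50 (80%) | 11.1 points | 67.0% to 88.8% | 66.3% to 90.0% |
| 45/50 (90%) | 8.3 points | 78.6% to 95.7% | 78.2% to 96.7% |
| 70/100 (70%) | 9.0 points | 60.4% to 78.1% | 60.0% to 78.8% |

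Half the width of the exact interval is (82.1 − 55.4)/2 = 13.4 points at 35/50, (90.0 − 66.3)/2 = 11.9 at 40/50, and (96.7 − 78.2)/2 = 9.3 at 45/50.

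**Comparison with the pilot.** Taking 70% of 17 as 12/17, the exact interval is 44.0% to 89.7%, a half-width of about 23 points. Going from 17 to 50 children narrows this to about 13, a real gain that the planned report would not show.

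**The case against.** The strongest reply is that nothing is hidden. The plan asks for counts as well as percentages, and the adherence denominator is defined, so any reader can work out an interval. The analysis paragraph is generic and does not forbid one. This is true and limits the seriousness of the point. Even so, an analyst following the text would report no interval, and the study's own conclusion would rest on the percentage.

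Several stronger readings are tempting, and the documents do not support them.

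- *That the sample-size section claims 50 is enough for tolerance.* Its closing remark directly follows a calculation labelled as progression and compares 50 with the resulting 38. The gap is that nothing is said about the primary objective.
- *That the 20% loss cuts the primary denominator to 40.* For adherence as defined, children who do not complete are the outcome and stay in the denominator. The first tolerance survey is a telephone call one month after delivery, well before a year's losses accrue.
- *That 70% is a pass mark, so the chance of reaching it by luck matters.* No section sets a threshold for tolerance or adherence.
- *That ±13 points is the study's precision.* It holds for 50 children and a rate near 70%. That rate is for reading tolerance in a small pilot, and the section on tolerance describes pilot subjects aged 18 to 24 and expects children to do better.

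It is also fair to say that a binomial interval covers sampling error only. It does not address the self-selection of families who choose the lens. Nor does it settle which adherence definition applies, since that section gives both missed visits and a good/bad classification based on the child's answer. Poor compliance with follow-up is also listed among the elimination criteria. The interval is therefore not the whole of the inference, but it is a part the plan omits.

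**Conclusion.** The point holds as a modest improvement to the analysis of the primary outcomes. The planned output is a count and percentage, no comparator makes the named tests usable for tolerance or adherence, and no precision is stated. Depending on the observed rate, the unreported 95% uncertainty with 50 children is about ±13 points at 70%, ±11 to 12 at 80% and ±8 to 9 at 90%. With 100 children it is about ±9 at 70%. An observed 35/50 would be compatible with a true rate only a little above one half.

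These figures assume that all 50 (or 100) children contribute and that the rates are illustrative. For tolerance the number answering may be smaller, because the questionnaire puts that question only to children who report wearing the glasses. The omission is the same at any rate or sample size. It does not make the 31, 38 or 50 wrong for their stated purpose.

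**What to change.** In Plan for analysing the results, add: *The proportions with good overall tolerance, with good reading and walking performance, and with adherence will each be reported as count, denominator and percentage with an exact (Clopper-Pearson) or Wilson 95% confidence interval, and conclusions will be based on the interval. Adherence is completion of the three scheduled visits; its denominator is all enrolled children who received the spectacles.* One interval method should be named in advance. For tolerance, the number of children answering and the time point should be stated.

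Optionally, in Sample and sample size, say that the calculation covers progression only and add the illustrative precision: with 50 children, about ±13 points at 70%, ±11 to 12 at 80% and ±8 to 9 at 90%. Reconcile the 50 children in that section with the 100 in Current state of research, since the precision depends on it.

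The cost is a few sentences, with no more patients, visits or data. The one drawback is that the primary result will look less precise than a percentage alone.
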